4.2.4. Safety Endpoints

Safety assessments include physical examination, vital signs, electrocardiogram (ECG), hematology, serum chemistry, cardiac markers, fasting lipid panel, pregnancy testing (for females of childbearing potential [FCBPs] only), adverse events (AEs), concomitant medications, concomitant procedures and transfusions. After screening, echocardiogram (ECHO)

or multi-gated acquisition (MUGA) scan, urinalysis and coagulation will be repeated as clinically indicated.

4.3. Stratification, Randomization, and Blinding

Randomization only applies to the Phase 2 part and will be carried out using an Interactive Web Response System (IWRS). Subjects with an IDH2 mutation will be randomized to receive oral AG-221 + SC azacitidine (Arm 1) versus SC azacitidine (Arm 2) in 2:1 ratio. Arm 1 will include a minimum of 66 subjects and Arm 2 will include a minimum of 33 subjects, (99 subjects total in both arms).

For the Phase 2 part, all subjects randomized will be stratified by primary (i.e., de novo) or secondary (progression of MDS or myeloproliferative neoplasms [MPN], or therapy-related) AML according to the WHO classification.

During Phase 1b and Phase 2 a retrospective central pathology review of all bone marrow aspirates and/or biopsies and peripheral blood smears, which are collected in subjects of the AG-221 (Phase 1b dose-finding and Phase 2 randomized stage) treatment arms during screening, will be conducted by personnel blinded to subject treatment to confirm eligibility. Bone marrow aspirate and/or biopsy and peripheral blood smear collected after the start of study treatment must be available for both local and central pathology review. The retrospective central pathology review will require a set of duplicate slides for each bone marrow collection time point including bone marrow aspirate (BMA), peripheral blood smear, and bone marrow biopsy (BMB) if performed. The central pathology review will be conducted by personnel blinded to study treatment.

4.4. Sample Size Determination

The Phase 1b dose-finding stage will enroll a total of approximately 24 subjects. Additional subjects may be enrolled in a dose level to replace subjects who are not evaluable for the primary endpoint, or for further exploring safety, PK, PK/pharmacodynamics, or preliminary clinical activity.

In Phase 1b AG-120 expansion stage, to ensure acceptable toxicity at the RCD, up to 15 subjects will be accrued into the AG-120 expansion phase. Based on a sample size of 18 AML subjects treated at RCD (i.e., 15 subjects in the dose expansion and around 3 subjects in the dose escalation), there is 95% probability of detecting 1 or more AEs with an underlying rate of 15%, and 85% probability of detecting 1 or more AEs with an underlying rate of 10%.

In Phase 2 AG-221 randomized stage, subjects with AML with IDH2 mutation will be randomized to receive oral AG-221 + SC azacitidine versus SC azacitidine in a 2:1 ratio. A minimum of 99 subjects will be randomized in this phase with 66 subjects in the oral AG-221 + SC azacitidine arm, and 33 subjects in the SC azacitidine monotherapy arm. The statistical comparisons will be conducted for oral AG-221 + SC azacitidine versus azacitidine monotherapy. Assuming an ORR of 30% in the azacitidine monotherapy and an ORR of 50% for oral AG-221 + SC azacitidine arm, the sample size of 66 subjects in AG-221 + SC azacitidine arm and 33 patients in SC azacitidine monotherapy arm will provide 75% power to detect a 20% difference in ORR at a two-sided type I error rate of 0.2. The multiple comparisons were not considered in the sample size calculation.

5. GENERAL STATISTICAL CONSIDERATIONS

5.1. Reporting Conventions

The following reporting conventions apply generally to tables, listings, and figures:

- Data from all study centers will be combined for analysis;
- In general, analyses for Phase 1b subjects will be done by AG-120 + AZA and AG-221 + AZA and by dose cohort in dose-finding, total in dose-finding, dose cohort in expansion (only for AG-120 + AZA), and total for AG-120 + AZA. For Phase 2, AG-221+AZA versus pooled AZA alone will be compared.
- P-values will be rounded to 4 decimal places; P-values that round to 0.0000 will be presented as '<0.0001' and p-values that round to 1.000 will be presented as '>0.9999
- Confidence intervals (CIs) will be presented as two-sided 95% CIs unless specified differently in specific analysis;
- Summary statistics will consist of the number and percentage of subjects (or cycles, if appropriate) in each category for discrete variables, and the sample size, mean, median, standard deviation, first quartile (Q1), third quartile (Q3), minimum, and maximum for continuous variables;
- All mean and median values will be formatted to one more decimal place than the measured value. Standard deviation values will be formatted to two more decimal places than the measured value;
- All percentages will be rounded to one decimal place. The number and percentage of responses will be presented in the form XX (XX.X%), where the percentage is in the parentheses. In case of zero frequency, the percentage will not be displayed;
- All listings will be sorted for presentation in order of treatment arm, study center, subject, and date/time of procedure or event and will be presented separately for each phase. Subjects who are screened but not randomized will be listed separately as a non-randomized group;
- All analysis and summary tables will have the analysis population sample size (i.e., number of subjects);
- The day of the first dose of any study drug will be defined as Day 1.
- Unless noted otherwise, baseline value will be defined as the last non-missing value prior to the start of study treatment on Day 1 of Cycle 1. For subjects who are randomized but not treated, the baseline will be the assessment value on or prior to randomization date.
- To summarize efficacy/safety data by visit, the post-baseline results will be summarized by the scheduled visit or the derived visit as appropriate.
- Calculation of Cycles:

The start date of each treatment cycle will be determined based on study drug exposure records and visit date for each subject. The start date of the first cycle will be the earliest date the subject receives any study drug. For the other cycles, the start date will be based on scheduled study visit date for each subject. Once the start dates, e.g., $S_1, S_2, S_3 \dots$ are determined, the end date of each cycle is calculated as the day before the start date of the following cycle, i.e., $E_i = S_{i+1} - 1$. The cycle number for each date of interest, e.g., adverse event (AE) or lab will be calculated based on event start date and the cycle window start and end dates. If an event date is on or after S_i and before S_{i+1} , the corresponding cycle number will be i .

In case cycle information is not appropriately collected in the electronic case report forms (eCRFs), then cycle may be derived using study day relative to the first dose day. All by cycle analysis will use the defined cycle.

5.2. Analysis Populations

5.2.1. Intent-to-Treat Population

The intent-to-treat (ITT) population includes all subjects who are randomized to treatment, regardless of whether they received treatment or not. This population is defined for the Phase 2 part only and will be used in most of the data analysis except for safety data analysis.

5.2.2. Modified Intent-to-Treat Population

The modified intent-to-treat (mITT) population includes all subjects who have met all inclusion and exclusion criteria and experienced no major protocol deviations during the study, received at least one cycle of study treatment and had at least one post-randomization treatment response assessment performed. Major protocol deviations leading to exclusion from the mITT population are defined as any of the following:

- Had at least one inclusion/exclusion criteria violation;
- Disease status at screening not confirmed by retrospective central review;
- Initial study treatment given is not the one assigned in randomization;
- Received protocol-prohibited concomitant medication.

This population is defined for the Phase 2 part only.

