- p Whenever response/diagnosis is assessed in the Follow-up Period (ie, every 8 weeks [ $\pm$  28 days]). See Section 6.3 for details.
- q Day 1 ( $\pm$  14 days) of every 3rd cycle (eg, Cycles 3, 6, 9, etc) or more frequently per standard institutional practice. Not necessary for the EOT Visit if last performed within 14 days.
- r Day 1 ( $\pm$  28 days) of every 6th cycle (eg, Cycles 6, 12, 18, etc) or more frequently per standard institutional practice. Not necessary for the EOT Visit if last performed within 28 days.
- s Continuous starting after signing ICF through 28 days after the last study treatment. See Section 6.4.1 for details.
- t Including type, number of units, reasons, and date of transfusions taken  $\leq$  8 weeks prior to the start of study treatment through 28 days after the last study treatment. Thereafter, transfusions will continue to be collected until the next AML therapy after discontinuation from study treatment, death, lost to follow-up, withdrawal of consent for further data collection, or the End of Trial, whichever occurs first.
- v In addition to the frequency specified in the table, samples will also be collected if clinically indicated (eg, confirmation of CR/CRi/CRp, morphologic relapse after CR/CRi/CRp, or progression by a repeated bone marrow assessment at least 1 month later) or required for toxicity assessment. A sample of bone marrow and peripheral blood must also be sent at these time points for central pathology review.
- w Within 7 days prior to Day 1 of Cycle 2. The assessment is not required at Day 1 of Cycle 1.
- x Within 7 days prior to Day 1 of Cycle 3. The assessment is not required at Day 1 of Cycle 4.
- y Within 7 days prior to Day 1 of Cycle 5 and Day 1 of every 2nd cycle thereafter (eg, Cycles 7, 9, etc).
- z Not necessary for the EOT Visit if last performed within 28 days.
- bb A bone marrow biopsy can be collected in conjunction with an aspirate if it is standard institutional practice. A bone marrow biopsy must be collected if adequate aspirate is not attainable.
- cc A standard cytogenetic metaPhase preparation will be prepared if the bone marrow aspirate is obtained for assessing CR, morphologic relapse, or progressive disease and will be sent to the local laboratory for cytogenetic analysis.
- dd Including diary cards. See Section 7.6 for details.

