### 6.2.3. End of Treatment

An EOT evaluation will be performed for subjects who are withdrawn from study treatment for any reason as soon as possible after the decision to permanently discontinue study treatment has been made. An administrative window of  $\pm 7$  days is permitted for the EOT Visit, unless noted otherwise. If a subject is discontinued during a regularly-scheduled visit, all EOT evaluations should be completed at that visit.

The following evaluations will be performed as specified in the Table of Events ([Table 4](#)). For each evaluation, the same parameters as required at screening or on Day 1 of Cycle 1 should be evaluated.

- Registration of treatment discontinuation in IWRS
- HRQoL outcomes (EORTC QLQ-C30 and EQ-ED-5L questionnaires)
- Study drug accountability (where applicable; refer to [Section 7.5](#))
- Study drug dispensing and administration (where applicable; refer to [Section 7](#))
- ECOG performance status

- Physical examination, vital signs, and body weight. Significant findings are to be reported on the appropriate eCRF page.
- The following laboratory assessments will be done locally:
  - ECHO or MUGA scan if clinically indicated
  - 12-lead ECG
  - A serum or urine (investigator’s discretion under local regulations)  $\beta$ -hCG pregnancy test (sensitivity of at least 25 mIU/mL) (for FBCPs only)
- The following laboratory assessments will be done centrally:
  - Urinalysis and/or coagulation test if clinically indicated
  - Hematology panel
  - Chemistry panel
  - Cardiac markers (not necessary for the EOT Visit if it was last performed within 14 days)
  - Fasting lipid panel (not necessary for the EOT Visit if it was last performed within 28 days)
- Evaluations of AEs, [REDACTED] concomitant medications, concomitant procedures, and transfusions (monitored through 28 days after the last study treatment)
- Clinical site staff should confirm if any transfusions were received by the subject (including any at outside local institutions in between study visits) prior to each IP administration via use of patient diary or other local procedure in place at the investigational site.
- Bone marrow aspirate and/or biopsy, peripheral blood smear and, if applicable, local cytogenetics, for response assessment (not necessary for the EOT Visit if it was last performed within 28 days)

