- Clinical site staff should confirm if any transfusions were received by the subject (including any at outside local institutions in between study visits) prior to each IP administration via use of patient diary or other local procedure in place at the investigational site.
- Survival follow-up every 4 weeks ( $\pm 7$  days) until death, lost to follow-up, withdrawal of consent for further data collection, or the End of Trial, whichever occurs first. Information on subsequent AML therapies should be collected at the same schedule as survival follow-up. Survival follow-up may be conducted by record review (including public records) and/or telephone contact with the subject, family, or the subject's treating physician where allowed by local regulations.
- Females of childbearing potential should avoid becoming pregnant for 4 months after the last study treatment, and male subjects should avoid fathering a child for 4 months after the last study treatment (6 months after the last dose of azacitidine in Canada).
- Bone marrow aspirate and/or biopsy, peripheral blood smear and, if applicable, local cytogenetics report, must be available for local review for assessing response or disease diagnosis, every 8 weeks ( $\pm 28$  days). In addition, ensure peripheral blood for hematology is collected at the time of every bone marrow collection.
- Response to treatment, per modified IWG, and HI will be assessed if bone marrow samples are collected for assessing response in subjects who discontinue study treatment prior to relapse or progression.

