#### **Modified Intent-to-Treat Population**

The mITT population includes all subjects who have met all inclusion and exclusion criteria and experienced no major protocol deviations during the study, received at least one dose of study treatment, and had at least one response assessment performed.

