##### **9.6.2. Phase 2 AG-221 Randomized Stage**

For subjects in Phase 2, response will be primarily assessed by investigator review.

All efficacy analysis will be performed in the ITT population. Key efficacy analysis will also be performed on the mITT and EAP as supportive evidence and to assess the robustness of the efficacy findings. Subjects will be analyzed according to randomized treatment group.

The primary efficacy endpoint ORR is defined as the rate of responses including CR, CRi, CRp, MLFS and PR that are assessed by investigator according to modified IWG AML response criteria. The ORR will be summarized by treatment group. The treatment difference in ORR will be tested using the Chi squared test at a two-side 0.2 level and in the ITT population. This test will provide the pivotal p-value for the comparison of the ORR of the oral AG-221 + SC azacitidine versus azacitidine mono therapy. Estimated response rate with 80% and 95% confidence intervals will also be provided.

**Event-free survival (EFS)** is defined as the interval from the date of randomization to the date of documented morphologic relapse, progression, or death from any cause, whichever occurs first. The analysis of the **EFS** will be conducted using the log-rank test in the ITT population. This test will be used for the comparison of the two EFS curves of oral AG-221+ SC azacitidine versus azacitidine mono therapy. The Cox proportional hazards regression model will be used to estimate the hazard ratio and a 95% confidence interval for the hazard ratio.

**Duration of response** is defined as time from the first documented CR/CRi/CRp/MLFS/PR to the date of the first documented morphologic relapse, progression according to modified IWG AML response criteria ([Appendix F](#)), or death due to any cause, whichever occurs first. Subjects without morphologic relapse, progression, or death due to any cause will be censored at the date of the last response assessment. Duration of response will be assessed using Kaplan-Meier methods. Point estimates and 95% CIs will be provided where appropriate for the median and other quantiles.

**Time to response** is defined as time from the date of first dose to the date of first occurrence of response, which includes CR, CRi, CRp, PR and MLFS as determined by investigator. Time to response will be summarized using descriptive statistics in subjects with documented CR, CRi, CRp, PR and MLFS as determined by the investigator.

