10.2. Analyses of Secondary Efficacy Endpoints

For Phase 1b, ORR and Sponsor Derived CR/CRh (based on laboratory dataset) are secondary efficacy endpoints and will be analyzed based on the FAP population and on the EAP as sensitivity analysis. These endpoints will be presented descriptively with 95% and 90% CI. Other measures of clinical activity, including duration of response, duration of CR/CRh, duration of remission, time to response, time to remission, time to CR/CRh, event-free survival (EFS), and overall survival may be summarized as appropriate in the FAP population.

For Phase 2, time-to-event secondary efficacy variables are displayed as part of [Table 2](#) (EFS, duration of response, OS, duration of remission (CR), and duration of sponsor assessed CR and CRh) will be analyzed by the KM method if appropriate to estimate time-to-event curves. In addition, Cox proportional hazards regression models will be generated to obtain hazard ratios and their two-sided 95% CI, and the p-value will be based on 2-sided log-rank test as appropriate. Time to response, time to remission, and time to sponsored assessed CR and CRh will be summarized

descriptively. Counts and percentages will be used to describe categorical variables. Rates, such as Complete remission rate, Hematologic improvement rate, sponsor derived CR and CR + CRh, will be analyzed similarly to ORR. All secondary efficacy endpoints for Phase 2 will be analyzed based on ITT population and on the mITT as supportive evidence and to assess the robustness of the efficacy findings. Subjects will be analyzed according to randomized treatment arm.

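### SAP 5.2.2 replaces the protocol's one-dose rule for mITT with an undefined one-cycle rule, which can drop early discontinuers from the Phase 2 supportive analyses

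*SAP*

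**What the plan says.** The two definitions differ on exposure. Protocol 9.2.3 admits to mITT an eligible subject without major deviations who "received at least one dose of study treatment, and had at least one response assessment performed". SAP 5.2.2 keeps the eligibility and deviation conditions but requires that the subject "received at least one cycle of study treatment and had at least one post-randomization treatment response assessment performed". The SAP gives no reason for the change.

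The SAP does not say what receiving a cycle means. Section 5.1 only dates cycles: "The start date of the first cycle will be the earliest date the subject receives any study drug". Elsewhere the SAP sets exposure at one dose, for the Safety, PK and full analysis populations (5.2.3 to 5.2.5).

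Both documents use mITT as a robustness set. Protocol 9.6.2 states: "Key efficacy analysis will also be performed on the mITT and EAP as supportive evidence and to assess the robustness of the efficacy findings". The SAP goes further. Section 10 runs Phase 2 efficacy analyses on mITT as well as ITT, 10.1 names mITT and the evaluable population (EAP) as sensitivity sets for ORR, and 10.2 says: "All secondary efficacy endpoints for Phase 2 will be analyzed based on ITT population and on the mITT as supportive evidence". EFS and OS are among those endpoints, and both are timed from randomisation.

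**The concern.** A supportive population should show whether the ITT result survives reasonable changes in who is counted. If membership depends on getting through about 28 days of treatment, it depends on something that happens after randomisation and that treatment can affect. This is an open-label comparison of azacitidine with and without an added drug, so early intolerance is one of the ways in which the arms could differ. A set that removes early stoppers could agree with ITT, or look better than ITT, because of the removal itself.

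The undefined term matters separately. Read as entering Cycle 1, the rule is the same as one dose. Read as completing Cycle 1, it is stricter. With 33 planned controls, that choice should be fixed in the text and not left to programming.

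**Working it through.** **Design figure.** Inputs from SAP 4.4: ORR 30% against 50%, 33 and 66 subjects, two-sided alpha 0.2, stated power 75%. The pooled rate is (33×0.30 + 66×0.50)/99 = 0.433. The standard error is 0.1057 under the null and 0.1008 under the alternative. Power = Φ[(0.20 − 1.2816×0.1057)/0.1008] = 73.9%. Exact enumeration of the uncorrected chi-square test gives 75.3%. The stated figure reproduces. It rests on ITT, so the mITT wording does not change it.

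**Who is excluded, and by which rule.** The first scheduled on-treatment response assessment is the marrow before Cycle 2: "Within 7 days prior to Day 1 of Cycle 2. The assessment is not required at Day 1 of Cycle 1" (Protocol Table 4, footnote w). Table 4 schedules no response assessment at screening, so I read the protocol's assessment condition as post-baseline, which the SAP states outright. An early stopper can still be assessed. Section 6.2.3 calls for marrow at the end-of-treatment visit "for response assessment (not necessary for the EOT Visit if it was last performed within 28 days"). Section 6.3 says that samples "must be available for local review for assessing response or disease diagnosis, every 8 weeks" for subjects who stopped before relapse, progression or second-line therapy.

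| Subject | Protocol mITT | SAP mITT, if a completed cycle is meant |
|---|---|---|
| Dies in Cycle 1 before any marrow | Out (no assessment) | Out (no assessment) |
| Stops in Cycle 1, never assessed | Out | Out |
| Stops in Cycle 1, assessed at EOT or in follow-up | In | **Out** |
| Dies or stops late in Cycle 1, after the pre-Cycle 2 marrow | In | **Out** |
| Completes Cycle 1 and is assessed | In | In |

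Only the two rows in bold are due to the SAP change.

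**Ceiling on the size.** The documents give no Cycle 1 loss rate. Let d be the total share excluded early, assumed to be 5-20%, with every excluded subject a non-responder. Then mITT ORR = ITT ORR/(1 − d).

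| d, control / combination | Control ORR | Combination ORR | Difference (points) |
|---|---|---|---|
| 0 / 0 | 30.0% | 50.0% | 20.0 |
| 5% / 5% | 31.6% | 52.6% | 21.1 |
| 10% / 10% | 33.3% | 55.6% | 22.2 |
| 20% / 20% | 37.5% | 62.5% | 25.0 |
| 5% / 15% | 31.6% | 58.8% | 27.2 |
| 15% / 5% | 35.3% | 52.6% | 17.3 |

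If both arms truly had a 30% ORR, losses of 5% and 15% alone would produce 0.30/0.85 − 0.30/0.95 = 3.7 points.

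**The part due to the SAP wording.** Let e be the share that the protocol rule already excludes. The increment is r/(1 − d) − r/(1 − e), where r is the ITT ORR. It is zero when e = d. As an illustration only, d = 20% and e = 15% give 37.5% − 35.3% = 2.2 points for control and 62.5% − 58.8% = 3.7 points for the combination. The documents supply neither d nor e.

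**The case against.** The case for leaving this alone has weight. The pivotal ORR test is in ITT, and so are EFS, OS and the other secondary endpoints. EFS has three further sensitivity analyses based on censoring rules (SAP 10.2.1). Reasons for exclusion from mITT are listed by subject (SAP 6), so selective exclusion would be visible. Early deaths and toxicity are reported in the one-dose safety population. Protocol Section 9 leaves final methods to the SAP. All of this stands, and it limits the consequence to supportive results.

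It does not remove the conflict. Two current documents define the same population differently, and the SAP neither explains nor defines its stricter term. EAP does not fill the gap, because it requires an assessment at Day 28 or later and so also omits most early deaths.

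A reader might infer that the SAP change is what removes Cycle 1 deaths. The documents do not support that: the assessment condition in both already removes anyone who died before a marrow was taken. A reader might also infer that every mITT subject has guaranteed event-free time. For EFS this is not so. Progression is dated to when a criterion is first met (SAP 17.4), which can fall in Cycle 1, and treatment may continue after progression (Protocol 11.1). On the completed-cycle reading, only survival through Cycle 1 is guaranteed, and the assessment condition already produces much of that.

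**Conclusion.** The conflict is real and should be resolved, but it is confined to supportive analyses. The SAP tightens the mITT exposure rule without a reason and in terms that can be read two ways. On the stricter reading it additionally loses assessed early discontinuers and late Cycle 1 deaths or stops, and that loss can differ by arm.

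The added loss cannot be sized from the documents. The rises to about 32-38% (control) and 53-63% (combination) are ceilings on total early exclusion. They assume 5-20% loss and no responders among those excluded. The second assumption is doubtful for the subjects affected here, who were assessed and may be followed for response after stopping. The direction between arms is also open: a 10-point imbalance in loss could move a 20-point difference to 17.3 or 27.2. It would be wrong to conclude that the rule must favour the combination, or that a full completed cycle is certainly meant. The primary analysis, alpha, sample size and power are untouched.

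**What to change.** In SAP 5.2.2, replace the one-cycle condition with the one-dose condition of Protocol 9.2.3. Keep the SAP's clarification that the response assessment is post-randomisation. Wherever mITT results are reported, describe them as conditional on having a response assessment, because restoring the dose rule does not bring back subjects who died before one. Removing the assessment condition for EFS and OS is not proposed: it would depart from the protocol's own mITT definition and is a matter of preference.

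The cost is SAP wording and possibly slightly less favourable supportive results. No change to sample size, alpha or the primary analysis is needed.
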